- a. Blood sample will be collected prior to vaccination.
- b. The subject may receive vaccines with inactivated poliovirus, hepatitis B, or *Haemophilus influenzae* type b (either separately or in the diphtheria, tetanus, and pertussis combination vaccine) at 2, 4, and 6 months of age. Measles, mumps, and rubella (MMR) vaccination may be administered concomitantly at 12 months of age or according to the permitted treatment windows in Section 5.7.3. Rotavirus vaccine may be administered orally at any time.
- c. The subject's legally acceptable representative will record prompted local reactions and systemic events in an e-diary for the 7 days following each dose of Prevnar 13 and c7vPnC Supplemental Dose. For the c7vPnC Supplemental Dose only, the subject's legally acceptable representative will be instructed to contact the study staff if the subject experiences redness or swelling >14 caliper units, severe pain at the injection site, or a fever >104.0°F (>40.0°C), or has an emergency room visit or hospitalization.
- d. Designated site staff will review e-diary data online at frequent intervals (daily is optimal) for the 7 days following each dose of Prevnar 13 and c7vPnC Supplemental Dose to evaluate subject compliance and reported events as part of the ongoing safety review.
- e. Record concomitant medications used to treat SAEs and NDCMCs as described in Section 5.7.4.
- f. A newly diagnosed chronic medical condition is defined as a disease or medical condition, not previously identified, that is expected to be persistent or otherwise long-lasting in its effects.

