3. STUDY DESIGN

This will be a Phase 2, multicenter, randomized, active-controlled, open-label study with a 3-arm parallel design, conducted at investigator sites in the United States. A total of 565 infants \ge 42 to \le 98 days of age at the time of consent will be enrolled and randomized in a 1:1:1 ratio to receive a vaccine series with:

- c7vPnC coadministered with Prevnar 13 (Group 1 coadministration);
- c7vPnC given 1 month after Prevnar 13 (Group 2 staggered administration); or
- Prevnar 13 alone as the active control group (Group 3 control with Supplemental Dose).
 A single dose of c7vPnC will be administered after the Prevnar 13 series is completed in this group.

In all groups, Prevnar 13 will be administered at 2, 4, 6, and 12 months of age. c7vPnC will be administered at 2, 4, 6, and 12 months of age in Group 1; at 3, 5, 7, and 13 months of age in Group 2; and at 13 months of age in Group 3. **Note:** In this document, and related study documents, vaccine (investigational product) Doses 1, 2, 3, and 4 specifically refer to the doses of c7vPnC administered in Groups 1 and 2, or the doses of Prevnar 13 administered in the control group (Group 3). The dose of c7vPnC administered in Group 3 will be referred to as the Supplemental Dose. See Table 1 for a summary of study groups and key procedures.

Table 1. Summary of Study Groups and Key Procedures

·	2 mo/o	3 mo/o	4 mo/o	5 mo/o	6 mo/o	7 mo/o	8 mo/o	12 mo/o	13 mo/o	14 mo/o	18 mo/o	19 mo/o
Group 1 Coadmin. c7vPnC (n= ~188)	c7vPnC Dose 1 Prev13		c7vPnC Dose 2 Prev13		c7vPnC Dose 3 Prev13	Blood draw		Blood draw c7vPnC Dose 4 Prev13	Blood draw		Phone contact	
Group 2 Staggered c7vPnC (n= ~188)	Prev13	c7vPnC Dose 1	Prev13	c7vPnC Dose 2	Prev13	Blood draw c7vPnC Dose 3	Blood draw	Prev13	Blood draw c7vPnC Dose 4	Blood draw		Phone contact
Group 3 Control (n= ~188)	Prev13 Dose 1		Prev13 Dose 2		Prev13 Dose 3	Blood draw		Blood draw Prev13 Dose 4	Blood draw c7vPnC Suppl. Dose	CCI		Phone contact

Abbreviations: Coadmin. = coadministered; mo/o = months old; Prev13 = Prevnar 13; Suppl. = supplemental.

Vaccine containing diphtheria, tetanus, and acellular pertussis antigens will be administered at 2, 4, and 6 months of age. This is as part of routine standard of care in the United States,

Other routine pediatric vaccines may be administered in this study, with or without certain restrictions.

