6.3. Group 3 (Control With Supplemental Dose) Study Procedures

6.3.1. Group 3 Visit 1 (Dose 1: 2-Month Visit, Day 1)

Prior to randomization:

- A personally signed and dated informed consent document indicating that the subject's legally acceptable representative has been informed of all pertinent aspects of the study before performing any study-specific procedures.
- Record the subject's demographic information (including date of birth, sex, race, and ethnicity).
- Obtain and record the subject's medical history including prior vaccinations.
- Perform physical examination evaluating any clinically significant abnormalities within the following body systems: general appearance; skin; head, eyes, ears, nose, and throat; heart; lungs; abdomen; musculoskeletal; extremities; neurological; and lymph nodes. Clinically significant abnormal results will be recorded in the CRF.
- Measure and record the subject's rectal temperature (°F/°C).
- Ensure that all inclusion criteria, none of the exclusion criteria, and none of the temporary delay criteria are met.
- Assign randomization number and investigational container number via the IRT. This must be the last step before proceeding. A site staff member will prepare the investigational product according to the IP manual.

After randomization:

• Administer a single 0.5-mL injection of Prevnar 13 into the left anterolateral thigh.

- Administer DTaP-containing vaccine and other permitted vaccines (to be administered into a limb other than the site of Prevnar 13 injection).
- Site staff will observe the subject for at least 30 minutes after vaccination for any acute reactions. Record any AEs on the CRF and on an SAE form as applicable. Record concomitant medications used to treat SAEs and NDCMCs.
- Issue the subject's legally acceptable representative a measuring device to measure injection site reactions and a digital thermometer and provide instructions on their use.
- Issue the subject's legally acceptable representative an e-diary (device or application). Provide instructions on use and completion of the e-diary. Ask the subject's legally acceptable representative to complete the e-diary from Day 1 to Day 7, with Day 1 being the day of vaccination.
- Ask the subject's legally acceptable representative to contact the investigator or investigator site staff as soon as possible if any significant illness or medical event (eg, emergency room visit or hospitalization) occurs.

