- Determine whether any AEs (includes nonserious AEs, SAEs, or NDCMCs) have occurred since the previous visit and follow up on any previously reported events to determine the outcome (ie, record stop dates or confirm if they are still continuing) and record as described in Section 8, and record concomitant medications used to treat SAEs and NDCMCs.
- Measure and record the subject's rectal temperature (°F/°C).
- Collect a blood sample of approximately 5 mL for immunogenicity prior to vaccination (a topical anesthetic is permitted).
- Administer a single 0.5-mL injection of c7vPnC into the left anterolateral thigh.

- Site staff will observe the subject for at least 30 minutes after vaccination for any acute reactions. Record any AEs on the CRF and on an SAE form as applicable. Record concomitant medications used to treat SAEs and NDCMCs.
- Confirm that the e-diary is working and review instructions if necessary. Remind the subject's legally acceptable representative to complete the e-diary from Day 1 to Day 7, with Day 1 being the day of vaccination. Provide thermometer or measuring device if needed.
- Ask the subject's legally acceptable representative to contact the investigator site staff or investigator as soon as possible during the 7-day postvaccination period if the subject experiences fever >104.0°F (>40.0°C), redness or swelling at the injection site measuring

- >14 measuring device units (>7 cm), or severe injection site pain (causes limitation of limb movement) to determine if the event requires further assessment by the investigator.
- Remind the subject's legally acceptable representative to contact the investigator or investigator site staff immediately if any significant illness or medical event (eg, emergency room visit or hospitalization) occurs.
- Remind the subject's legally acceptable representative that use of prophylactic antipyretic/pain medication, while permitted, is not recommended on the day of investigational product administration (before or after vaccination).
- The investigator or an authorized designee completes the CRF and updates the investigational product accountability records.

6.3.7. Group 3 Visit 7 (Follow-up of the Supplemental Dose: 14-Month Visit, 28 to 42 Days After the Supplemental Dose)

- Ensure and document that the subject continues to be eligible for the study (see Section 6.5 for withdrawal information), and none of the temporary delay criteria are met.

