6.4. Unscheduled Visits

If the subject's legally acceptable representative reports redness or swelling at the injection site measuring >14 measuring device units (>7 cm) or severe injection site pain or a fever >104.0°F (>40.0°C) during the 7-day postvaccination period of c7vPnC Doses 1 to 4 and the Supplemental Dose, a telephone contact must occur as soon as possible between the investigator or medically qualified designee and subject's legally acceptable representative to assess if an unscheduled investigator site visit is required. Note that for a fever >104.0°F (>40.0°C), the subject's legally acceptable representative should be instructed not to delay seeking medical care, as appropriate, while arranging for an unscheduled visit. An investigator site visit should be scheduled as soon as possible to assess the extent of the reaction unless any of the following is true:

- The subject's legally acceptable representative is unable to bring the subject to the unscheduled visit.
- The reaction is no longer present at the time of the telephone contact.
- The subject's legally acceptable representative recorded an incorrect value in the e-diary (confirmation of an e-diary data entry error).
- The principal investigator (PI) or authorized designee determined it was not needed.

This telephone contact will be recorded in the subject's source documentation and the CRF.

If the subject's legally acceptable representative is unable to bring the subject to an unscheduled visit, or the PI or authorized designee determined it was not needed, any ongoing reactions must be assessed at the next study visit.

During the investigator site visit, the reactions should be assessed by the investigator or a medically qualified member of the study staff such as a study physician or a study nurse, as applicable to the investigator's local practice, who will:

- Measure rectal temperature (°F/°C).
- Measure minimum and maximum diameters of redness (if present).
- Measure minimum and maximum diameters of swelling (if present).
- Assess injection site pain in accordance with the grades provided in Section 7.1.2 (if present).
- Assess for other findings associated with the reaction and record on the AE page of the CRF, if appropriate.

The investigator or an authorized designee will complete the unscheduled visit assessment page of the CRF.

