7.1.2.1. Local Reactions

For the first 7 days following Doses 1 to 4 and the Supplemental Dose, the subject's legally acceptable representative will be asked to assess redness, swelling, and pain at the injection site and to record the symptoms in the e-diary in the evening. Redness and swelling will be measured and recorded in measuring device units (range: 1 to >14; an entry in the e-diary of 15 will denote >14), and then categorized during analysis as mild, moderate, or severe based on the grading scale in Table 2 below. Measuring device units can be converted to centimeters according to the following scale: 1 measuring device unit = 0.5 cm. Pain at the vaccine injection site will be assessed by the subject's legally acceptable representative as mild, moderate, or severe according to the grading scale in Table 2 below. The subject's legally acceptable representative will be prompted to contact the investigator if the subject experiences a severe (Grade 3 or above) local reaction to assess the reaction and perform an unscheduled assessment or visit as appropriate.

Only an investigator is able to classify a subject's local reaction as Grade 4, after physical examination of the subject or documentation from another medically qualified source (eg, emergency room or hospital record). If a subject experiences a Grade 4 local reaction, the investigator must immediately notify the sponsor. Site staff will educate the subject's legally acceptable representative regarding signs and symptoms that would prompt site contact.

The procedure for notification of the sponsor is provided in the study reference manual (SRM) or equivalent.

Table 2. Grading Scales for Local Reactions

	Mild Grade 1	Moderate Grade 2	Severe Grade 3 ^a	Grade 4 ^b
Redness (synonymous with erythema)	1 to 4 caliper units (or measuring device units)	5 to 14 caliper units (or measuring device units) =	>14 caliper units (or measuring device units) =	Necrosis or exfoliative dermatitis
Swelling (synonymous with edema)	0.5 to 2.0 cm 1 to 4 caliper units (or measuring device units) = 0.5 to 2.0 cm	>2.0 to 7.0 cm 5 to 14 caliper units (or measuring device units) = >2.0 to 7.0 cm	>7 cm >14 caliper units (or measuring device units) = >7 cm	Necrosis

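### The protocol contradicts itself on follow-up of severe local reactions and fever above 104.0°F after Group 3's Prevnar 13 Doses 1 to 4

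*Protocol*

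**What the plan says.** Protocol Section 3 fixes the vocabulary. Doses 1 to 4 mean the c7vPnC doses in Groups 1 and 2, "or the doses of Prevnar 13 administered in the control group (Group 3"). The single c7vPnC dose in Group 3 is the Supplemental Dose.

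One set of passages leaves the Group 3 Prevnar 13 doses out of the follow-up rule:

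- Schedule of Activities, Group 3, footnote c: "For the c7vPnC Supplemental Dose only, the subject's legally acceptable representative will be instructed to contact the study staff". The triggers are redness or swelling above 14 caliper units, severe pain, fever above 104.0°F, and an emergency room visit or hospitalization.
- Sections 6.3.1, 6.3.2, 6.3.3 and 6.3.5 (Group 3, Doses 1 to 4) carry only the general request to "contact the investigator or investigator site staff as soon as possible if any significant illness or medical event" occurs. The specific severe-reaction and fever instruction first appears in Group 3 at the Supplemental Dose visit (Section 6.3.6): "Ask the subject's legally acceptable representative to contact the investigator site staff or investigator as soon as possible during the 7-day postvaccination period".
- Section 6.4 sets out what happens after a report in the "7-day postvaccination period of c7vPnC Doses 1 to 4 and the Supplemental Dose, a telephone contact must occur as soon as possible". The same paragraph says that for fever above 104.0°F "the subject's legally acceptable representative should be instructed not to delay seeking medical care, as appropriate, while arranging for an unscheduled visit".

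Another set applies the rule without a product limit:

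- Section 7.1.2.1 covers assessments "For the first 7 days following Doses 1 to 4 and the Supplemental Dose" and says that the representative "will be prompted to contact the investigator if the subject experiences a severe (Grade 3 or above) local reaction", with an unscheduled assessment or visit as appropriate.
- Table 2 footnote a requires the site to contact representatives of subjects with reactions above 14 caliper units.
- Section 7.1.2.2.2 collects temperature after the same doses and attaches contact and an unscheduled assessment to high fever.

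**The concern.** The two sets of text give a site different instructions for the same event. An infant in Group 3 with severe injection-site pain or a fever above 104.0°F after a Prevnar 13 dose falls inside Section 7 but outside footnote c, the visit procedures and Section 6.4.

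This matters because describing safety is the primary objective, the trial is open-label, and Group 3 is the active control. The Section 6.4 pathway also affects the data. The telephone contact can expose an e-diary entry error. The visit re-measures the reaction and can put associated findings on the AE page. A Grade 4 local reaction can be classified only by an investigator, after examination or from medical documentation (Section 7.1.2.1). If these steps are structured for c7vPnC doses and left open for control doses, ascertainment is uneven by design.

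There is also a protection point. The advice not to delay care for high fever sits in the c7vPnC-limited paragraph, yet control infants receive Prevnar 13 together with a DTaP-containing vaccine at 2, 4 and 6 months (Section 5.7.1).

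**Working it through.** The plan gives no figure to reproduce. The check is a comparison of text, followed by a count of how many vaccinations the conflict touches.

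**Text comparison for Group 3, Prevnar 13 Doses 1 to 4**

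| Place in protocol | Severe-reaction/high-fever rule applies? |
|---|---|
| Schedule of Activities, Group 3, footnote c | No: Supplemental Dose only |
| Sections 6.3.1, 6.3.2, 6.3.3, 6.3.5 | No: general illness request only |
| Section 6.4, telephone contact, visit and care-seeking advice | No: c7vPnC doses only |
| Section 7.1.2.1 | Yes |
| Table 2 footnote a (size trigger) | Yes: no product limit |
| Section 7.1.2.2.2 (fever) | Yes |

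Reading the Section 7 prompt as an e-diary alert and the footnote c instruction as spoken advice does not reconcile them. Section 7 ties an unscheduled assessment to the prompt, and Table 2 footnote a puts the contact duty on the site.

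Footnote c has a second inconsistency. It lists emergency room visits and hospitalization under the Supplemental Dose limit, while Sections 6.3.1 to 6.3.3 and 6.3.5 and the later paragraphs of Section 6.4 ask for those reports with no such limit.

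**Count of e-diary doses**

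- Per infant, Section 6.4 covers 4 of 4 in Group 1, 4 of 4 in Group 2 and 1 of 5 in Group 3.
- Inputs: 188 infants per arm and 15% dropout by Dose 3 (Section 3.3). Assumption: dropout is linear up to Dose 3, with none afterwards.
- Group 3 Prevnar 13 dose-occasions: 188 + 188 × 0.925 + 188 × 0.85 + 188 × 0.85 = 188 + 173.9 + 159.8 + 159.8 = 681.5.
- Adding the Supplemental Dose: 681.5 + 159.8 = 841.3. Share outside Section 6.4: 681.5 / 841.3 = 81.0%.
- With no dropout: 4 × 188 = 752 of 5 × 188 = 940, or 80.0%.
- Share of all e-diary dose-occasions in the trial: 681.5 / (681.5 + 681.5 + 841.3) = 681.5 / 2204.3 = 30.9%; with no dropout, 752 / 2444 = 30.8%.

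**Number of reports, under an assumed trigger rate**

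The documents give no rate for these triggers. At an assumed 0.5% to 2% of doses, the number of control reports outside the Section 6.4 rule runs from 681.5 × 0.005 = 3.4 to 752 × 0.02 = 15.0, so about 3 to 15 over the study.

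**The case against.** The strongest reply is that the narrower rule looks deliberate. Footnote c says it outright, and the Group 3 visit procedures and Section 6.4 agree with it. Section 6 is written by group, whereas Section 7.1.2 is a grading section written once for everybody. Closer contact for an unlicensed product than for a vaccine licensed in the United States since 2010 is a defensible choice. Group 2 supports this reading, since its Prevnar 13 visits carry neither an e-diary nor the severe-reaction instruction.

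That explains the wording but does not remove the conflict. The protocol gives no rationale for the difference and no order of precedence. Section 7.1 sends the reader to the Schedule of Activities, to Section 8 and to its own text alike. Section 5 also makes Prevnar 13 an investigational product in this study.

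The objection is right about the size of the consequence. A reader might infer that control families receive no guidance on severe reactions and that site contact after control doses is purely optional. The documents do not support that. Table 2 footnote a obliges the site to make contact for reactions above 14 units in any group, and Section 7.1.2.1 has staff educate families on what should prompt contact. Section 6.4 is silent on Prevnar 13 doses; it does not forbid contact.

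It is also true that limiting the Section 7 sentences to c7vPnC would remove the contradiction. The wider rule is preferable because it gives even ascertainment for a primary safety endpoint and the same fever advice to control infants, at little cost.

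**Conclusion.** The contradiction stands on the current text and should be corrected. It does not rest on redaction, text extraction or the amendment log. Sites that follow footnote c and Section 6.4 would follow up control e-diary doses less closely than c7vPnC doses.

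The effect is limited. Prompted reactions are recorded in the e-diary after every Group 3 dose and reviewed online (Group 3 footnote d; Section 7.1.1), and reports of emergency room visits and hospitalization are requested in all groups.

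A reader might take the 81%, 31% and 3 to 15 figures as missed events or as a bias in the displayed rates. They are neither. The percentages count vaccinations outside one section, under a stated dropout pattern, and the report count adds a trigger rate that has no source in the documents. No change in reported rates is claimed. What is at issue is consistent instruction, even follow-up for the primary objective, and equal fever advice for control infants.

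**What to change.** Amend Group 3 footnote c and Sections 6.3.1, 6.3.2, 6.3.3, 6.3.5 and 6.4 to match Section 7. The same rule should then apply after every e-diary dose in all three groups: the family's contact instruction, the telephone contact, the unscheduled-assessment pathway, and the advice not to delay care for fever above 104.0°F. Take emergency room visits and hospitalization out of the Supplemental Dose limit in footnote c.

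Group 2's Prevnar 13 doses have no e-diary and would stay outside the rule, so the change aligns e-diary doses and not every Prevnar 13 dose.

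The cost is protocol wording and a few extra telephone contacts in Group 3: at most about 3 to 15 under the assumed trigger rate, and fewer where Table 2 footnote a already requires the contact. The investigator can still waive visits under Section 6.4. No endpoint, analysis population or SAP text changes.

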1. INTRODUCTION

1.1. Indication

Complementary 7-valent pneumococcal conjugate vaccine (c7vPnC) is being developed for:

 Active immunization to prevent disease caused by the Streptococcus pneumoniae serotypes in the vaccine.

1.2. Background and Rationale

1.2.1. Pneumococcal Disease

S pneumoniae are gram-positive encapsulated cocci that are a leading cause of bacteremia, bacterial meningitis, pneumonia, and acute otitis media (AOM) and continue to be a major global public health concern. 1,2,3 Serious pneumococcal disease may occur at any age; however, children <5 years and adults ≥65 years of age are at particularly increased risk. 4 Individuals with certain comorbidities and immunocompromising conditions are also at risk, especially persons with chronic heart, lung, liver, and renal disease, as well as those who are functionally asplenic. The global burden of pneumococcal disease has been substantially impacted by pneumococcal conjugate vaccines. S pneumoniae caused an estimated 14.5 million cases of serious disease and 826,000 deaths annually in children <5 years of age prior to introduction of pneumococcal conjugate vaccines. A recent estimate suggested that in 2015, several years following introduction of pneumococcal conjugate vaccines into the national infant immunization programs of more than 100 countries, the global disease burden had declined, but S pneumoniae still accounted for 2.6 million cases of severe pneumococcal disease, 332,000 deaths in children <5 years of age, and 11% of deaths in children between the ages of 1 and 5 years. 5

The overall invasive pneumococcal disease (IPD) burden was estimated in 2014 to have decreased approximately 90% in the population <5 years of age in the United States since the introduction of pneumococcal conjugate vaccines.⁶ Even after the introduction of Prevnar 13[®] (13-valent pneumococcal conjugate vaccine), a significant proportion of IPD cases in persons <18 years of age is associated with hospitalization (71%), with a case fatality rate of 3%. This is due to the decrease in disease due to the serotypes in Prevnar® (7-valent pneumococcal conjugate vaccine) and Prevnar 13; however, disease due to serotypes not covered by those vaccines remains, and causes significant morbidity and mortality. Pediatric surveillance studies conducted between 2007 and 2013 in 8 US children's hospitals, and between 1997 and 2010 in a referral center in Utah, found case fatality rates of 10% and 13% with pneumococcal meningitis, respectively. These studies also found that between 52% and 63% of children surviving pneumococcal meningitis experience neurologic sequelae.^{8,9} Surveillance studies conducted in 2010-2012 by the Centers for Disease Control and Prevention (CDC) found that S pneumoniae remains among the most common pathogens identified in community-acquired pneumonia (CAP) requiring hospitalization in the United States in both children and adults. ^{10,11} These data suggest that S pneumoniae remains an important cause of serious disease in the United States and worldwide.

AOM is a common childhood illness, with the 2011 visit rates of 0.82 and 0.81 visits for AOM/child-year in children <2 years of age and 2 to 6 years of age, respectively, and represents a significant medical burden. While AOM is generally not considered a serious disease, it does carry the risk of more serious complications. These complications can range from the development of chronic or recurrent otitis media necessitating surgical intervention (tympanostomy tube placement), and accompanied by hearing losses with potential developmental and language delays, to invasive extension leading to mastoiditis and meningitis.

Although the introduction of pneumococcal conjugate vaccines into the US and other national infant immunization programs has brought about substantial reductions in the various manifestations of pneumococcal disease in pediatric (and to some extent adult) populations, a substantial burden of pneumococcal disease remains.

